1. PROTOCOL SUMMARY

1.1 Schedule of Activities (SoA)

1. Participants will be screened for eligibility with medical history, physical exam, prior treatment, history of anemia and blood tests including baseline CBC, reticulocyte count, ferritin, B-12 and serum folate level
2. If inclusion criteria are met and after signing a consent form, participants will start olaparib 300 mg twice daily, commercially approved
3. Assessment of CBC/serum folate will occur every 2 weeks for the first 3 months and then monthly for a total of 6 months from the time of enrollment onto study therapy. If the patient develops folate deficiency and requires folate replacement, CBC/serum folate and reticulocyte count will occur every 2 weeks for 12 months.
4. One-time measurement of serum folate to occur one month after completion or discontinuation of therapy with olaparib
5. If folate deficiency is identified (defined as any level below normal) at any time point, the following parameters will be assessed in 2 weeks or at the next visit/assessment point: a repeat CBC/serum folate level along with B-12, LDH, reticulocyte count, methylmalonic acid, and homocysteine. These labs (CBC/serum folate level, B-12, LDH, reticulocyte count, methylmalonic acid, and homocysteine) need to be drawn once- 2 weeks after initial folate deficiency is identified for confirmation purposes and to rule out co-existing B-12 deficiency or other causes of anemia.
6. Once folate deficiency is confirmed in the setting of hemoglobin (Hgb) less than 12 g/dl but above 10.0 g/dl, patients will be randomized to folate supplementation or placebo. At that point, assessment of CBC/reticulocyte count and folate levels will continue every 2 weeks.
7. If Hgb is above 12.0 g/dl and no folate deficiency is identified, patients will not be randomized. Assessment of CBC/serum folate will continue every 2 weeks for the first 3 months and then monthly for a total of 6 months from the time of enrollment onto the study.
8. If folate deficiency is identified in setting of Hgb less than 10.0 g/dl, patients will not be randomized but will receive folic acid supplementation at 1 mg daily. These patients will have weekly assessments of CBC/reticulocyte count and folate levels until Hgb improves to a level above 10.0 g/dl. At that point, assessment of CBC/reticulocyte count and folate levels will change back to every 2 weeks. However, folic acid replacement will continue as initiated.
9. If a patient is already on folic acid supplements and continues to experience folate deficiency with a Hgb less than 10.0 g/dl, then folic acid dose can be increased to 2 mg daily or higher, at the discretion of the investigator. These patients will have weekly assessments of CBC/reticulocyte count and folate levels until Hgb improves to greater than 10.0 g/dl. At that point, assessment of CBC/reticulocyte count and folate levels will change back to every 2 weeks. However, folic acid replacement will continue at the last dose.
10. If folate deficiency is identified again in a patient who is already on folic acid supplementation, the following parameters will be assessed in 2 weeks or at the next

Clinical Study Protocol - 6
 Olaparib - ESR-18-13807

visit/assessment point: a repeat CBC/serum folate level along with B-12, LDH, reticulocyte count, methylmalonic acid, and homocysteine (see item # 5).

11. Tumor assessment will be performed as per treating physicians decision and would include regular clinical exams, tumor marker monitoring, and imaging (body CT scans) at every 3 -6 month interval
12. Safety assessments will be performed at every clinic visit
13. Data on *BRCA* testing results (if performed as standard of care) will be collected at the time of enrollment and updated throughout the study duration.

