2. OBJECTIVES AND ENDPOINTS

Primary objective:

To determine the frequency and timing of folate deficiency in patients with solid tumors harboring molecular alterations such as germline and somatic mutations in *BRCA1* and *BRCA2* genes, other genes in Homologous DNA Recombination Repair (HRR) pathway, genomic stability as determined by Homologous Recombination Deficiency (HRD) assay, etc., who are treated with olaparib.

Secondary objectives:

To evaluate the effect of folic acid supplementation on serum folate, hemoglobin level, transfusion needs/number of transfusions, and need for olaparib treatment interruption, dose reduction and drug discontinuation.

To assess response rate (RR) to olaparib as it relates to serum folate level and folic acid supplementation.

Clinical Study Protocol - 6
Olaparib - ESR-18-13807

To assess progression-free survival (PFS) as it relates to serum folate level and folic acid supplementation.

Exploratory objectives:

To elucidate the mechanism of folate deficiency in patients treated with olaparib including possible interaction with germline *BRCA1* and *BRCA2* mutations via testing for folate receptors using immunohistochemistry on available paraffin embedded tumor samples from enrolled patients.

Primary endpoint:

The primary binary endpoint of the study is the percentage of patients who develop drug-induced folate deficiency, defined as serum folate level <7 ng/mL, within three months from start of olaparib therapy.

Secondary endpoints:

To assess the impact of folic acid supplementation on anemia, need for transfusion, and olaparib treatment interruption, dose reduction and drug discontinuation as compared to those who did not receive/require folic acid supplementation

To determine tumor response rate (RR), using treating physician assessment, on olaparib therapy in patients who develop folate deficiency and receive folic acid supplementation as compared to those who do not receive/require folic acid supplementation. Will also compare RR to historical controls (patients with solid tumors treated with olaparib or other approved agents on clinical trials).

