3. STUDY DESIGN

3.1 Overall design

This is a pilot, multi-center study evaluating the prevalence and timing of folate deficiency in patients with advanced solid tumors who are eligible to receive olaparib.

If patients develop folate deficiency concomitantly with a Hgb less than 12.0 g/dl (grade 1), they will then be randomized to receive either a placebo or folate supplementation.

All randomized patients who develop a Hgb less than 10 g/dl (grade 2) concomitantly with folate deficiency will receive folic acid supplementation irrespective of their prior randomization. If such patients were originally randomized to receive folic acid and continue to have a Hgb less than 10 g/dl and folate deficiency despite folate supplementation, folic acid dose will be increased to 2 mg daily or higher at the discretion of the investigator.

Patients will continue with olaparib until objective disease progression (determined by treating physician assessment) as long as in the Investigator's opinion they are benefiting from treatment and they do not meet any other discontinuation criteria.

For an overview of the study design see Figure 1, Section 1.3. For details on treatments given during the study, see Section 5.1 Treatments Administered.

For details on what is included in the efficacy and safety endpoints, see Section 2 Objectives and Endpoints.

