4.2 Exclusion criteria

Medical conditions

1. Patients with folic acid deficiency, defined as folate <7 ng/mL, or those taking folic acid supplementation within 30 days of olaparib initiation.
2. Other malignancy unless curatively treated with no evidence of disease for ≥ 5 years except: adequately treated non-melanoma skin cancer, curatively treated in situ cancer of the cervix, ductal carcinoma in situ (DCIS), Stage 1, grade 1 endometrial carcinoma. Patients with a history of localised triple negative breast cancer may be eligible, provided they completed their adjuvant chemotherapy more than three years prior to registration, and that the patient remains free of recurrent or metastatic disease
3. Persistent toxicities (>Common Terminology Criteria for Adverse Event (CTCAE) grade 2) caused by previous cancer therapy, excluding alopecia.
4. Patients with myelodysplastic syndrome/acute myeloid leukaemia or with features suggestive of MDS/AML.

Clinical Study Protocol - 6
Olaparib - ESR-18-13807

5. Patients with symptomatic uncontrolled brain metastases. A scan to confirm the absence of brain metastases is not required. The patient can receive a stable dose of corticosteroids before and during the study as long as these were started at least 4 weeks prior to treatment. Patients with spinal cord compression unless considered to have received definitive treatment for this and evidence of clinically stable disease for 28 days.
6. Patients considered a poor medical risk due to a serious, uncontrolled medical disorder, non-malignant systemic disease or active, uncontrolled infection. Examples include, but are not limited to, uncontrolled ventricular arrhythmia, recent (within 3 months) myocardial infarction, uncontrolled major seizure disorder, unstable spinal cord compression, superior vena cava syndrome, extensive interstitial bilateral lung disease on High Resolution Computed Tomography (HRCT) scan or any psychiatric disorder that prohibits obtaining informed consent.
7. Patients unable to swallow orally administered medication and patients with gastrointestinal disorders likely to interfere with absorption of the study medication.
8. Immunocompromised patients, e.g., patients who are known to be serologically positive for human immunodeficiency virus (HIV).
9. Patients with known active hepatitis (i.e. Hepatitis B or C).

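### Folate deficiency is an unnumbered below-normal value for confirmation, randomisation and folic acid, but <7 ng/mL for eligibility and the primary endpoint, and the two are never reconciled

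*Combined protocol and SAP*

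**What the plan says.** Two descriptions of folate deficiency stand in the current text.

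- **Acting on it.** Section 1.1, item 5: "If folate deficiency is identified (defined as any level below normal) at any time point". This starts the two-week repeat tests. Item 6 sends patients to randomisation: "Once folate deficiency is confirmed in the setting of hemoglobin (Hgb) less than 12 g/dl but above 10.0 g/dl". Item 8 gives open treatment: "If folate deficiency is identified in setting of Hgb less than 10.0 g/dl, patients will not be randomized but will receive folic acid supplementation". Neither item has a folate cut-off of its own.
- **Counting it.** Section 4.2, exclusion 1: "Patients with folic acid deficiency, defined as folate <7 ng/mL". Section 2, primary endpoint: "drug-induced folate deficiency, defined as serum folate level <7 ng/mL, within three months from start of olaparib therapy". Section 7.1.1, the synopsis (Section 1.2) and the sample size (Section 8.2) also use <7 ng/mL.

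Sections 3.1 and 8.4.1 use the term for randomisation, and Section 8.5 implies it for the accrual look at 30 patients, all without a number. Section 3.1 describes the setting: "This is a pilot, multi-center study evaluating the prevalence and timing of folate deficiency". No visible text states the lower limit of normal for folate, equates it with 7 ng/mL, or names one laboratory for the assay. Appendix A mentions a central laboratory, but only for liver tests.

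**The concern.** The trigger for the intervention and the event being counted should be the same thing, or differ in a stated way. Here the trigger depends on a reference limit that may vary between sites, while the event is a fixed number. Folate and blood counts are taken every two weeks over the same three months that define the primary endpoint, so folic acid can start inside that window and change whether the event occurs.

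The analysis population (Section 8.3) keeps everyone who took a dose of olaparib. Nothing says how to count a patient who starts folic acid before any value <7 ng/mL. At stake are the primary percentage, the make-up of the randomised group, and the decision at 30 patients on whether to continue accrual.

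**Working it through.** **1. The plan's own figure.** Inputs from Section 8.2: null rate 0.50, assumed rate 0.66 (measured at <7 ng/mL), one-sided alpha 0.05, power 80%, attrition 20%.

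- Normal approximation: n = [(1.645 × √(0.50 × 0.50) + 0.842 × √(0.66 × 0.34)) / 0.16]² = 58.2, so 59.
- Exact binomial at n=60: reject at 37 or more events; alpha 0.046, power 0.802. Rejecting at 36 would give alpha 0.078, so the boundary cannot be relaxed.
- Attrition: 60 / (1 − 0.20) = 75.

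The stated 60 and 75 are reproduced.

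**2. What follows from the local lower limit L.** The documents do not give L, so there are three cases.

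| L | Patient with folate between L and 7 | Consequence |
|---|---|---|
| Above 7 | Eligible and not a primary event, but deficient under item 5 | If the Hgb condition is met, may receive folic acid before any value <7; a later primary event may be prevented |
| Below 7 | A primary event, but not deficient under item 5 | With Hgb 10–12 g/dl, no confirmation or randomisation unless a later sample falls below L |
| Exactly 7 | None | No practical effect |

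In the first case, Section 4.1 admits patients with Hgb from 10 g/dL. Someone entering with Hgb between 10 and 12 and folate between 7 and L could therefore be confirmed and randomised with no fall in folate on olaparib.

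**3. Size of the first case, by assumption only.** Suppose early folic acid lowers the observed rate by d points. Exact power is P(X ≥ 37) for X ~ Binomial(60, 0.66 − d).

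| Assumed loss d | Observed rate | Events prevented (60 × d) | Exact power |
|---|---|---|---|
| 0 | 66% | 0 | 0.80 |
| 3 points | 63% | 1.8 | 0.64 |
| 5 points | 61% | 3 | 0.51 |
| 10 points | 56% | 6 | 0.23 |

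**4. How demanding those losses are.** Following Section 1.1, a prevented event needs a patient who has folate between 7 and L, meets the Hgb condition, receives folic acid, and would otherwise have fallen below 7 within three months. With Hgb 10–12 g/dl the patient must also be confirmed at the two-week repeat without already having dropped below 7. Allocation is 1:1 (Section 8.4.1), so through randomisation alone, 3 or 6 prevented events need about 6 or 12 such patients randomised, with folic acid fully protective. Planned events are 60 × 0.66 = 39.6, so 12 is about 30% of them. Open treatment at Hgb below 10 avoids the halving.

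**The case against.** The strongest reply is that the protocol has one meaning in mind. The figure <7 ng/mL recurs in five places, exclusion 1 removes patients below it, and those who enter follow a schedule headed for patients with normal folate. Normal would then mean 7 or more, and item 5 would be loose wording. Figure 1 is not shown in the text available, so whether it carries a cut-off cannot be checked. This is a plausible account of intent, but item 5 is the operative instruction to sites, and a site following it would apply its own laboratory's limit.

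The rest of the reply largely stands, and it rules out stronger readings a reader might infer:

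- **That power will fall to 0.51 or 0.23.** Those losses are assumed. The Hgb condition, the two-week confirmation and the 1:1 split make the larger ones extreme.
- **That every primary event between a lower local limit and 7 is lost from the randomised comparison.** Folate is retested every two weeks for three months and then monthly, so a patient may cross the local limit later. Under Section 1.1, patients with Hgb above 12 or below 10 g/dl are not randomised under either definition.
- **That the definitions alone separate the randomised and deficient groups.** Randomisation requires anaemia as well, so the groups differ by design.
- **That the randomised comparison is biased.** Both arms share one entry rule. A local limit changes who enters and how many, not the fairness of the allocation.

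**Conclusion.** The point holds as an unreconciled definition that affects the primary endpoint, entry to randomisation and the accrual look. Confidence is high that the texts conflict and low on the size of any bias, because the local limits are not in the documents. The direction depends on the limit: above 7, the primary percentage may be biased down; below 7, some events with Hgb 10–12 g/dl do not enter the randomised part; at 7, there is no effect.

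The power range of 0.64 to 0.23 rests on assumed losses of 3 to 10 points and on the anaemia conditions as given in Section 1.1. It shows that the design has little slack; it is not a forecast. The documents do not support calling the sample size wrong.

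**What to change.** Reconcile Section 1.1 (item 5, and through it items 6 and 8), Section 2, Section 4.2 and Section 7.1.1 to one explicit numeric study definition of folate deficiency, applied at all sites.

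- Keep <7 ng/mL for the primary endpoint and state it for the 30-patient look in Section 8.5. The 66% was measured at that value, so n=60 and 75 stay as they are. The documents give no rate for any other limit.
- Which limit governs giving folic acid is for the sponsor to decide. If it differs from the endpoint value, the protocol should say so.
- Record each site's folate reference limit.
- Add a sensitivity analysis of the primary percentage for patients who start folic acid before any value <7 ng/mL: for example, count them as events, and separately estimate the three-month percentage with censoring at folic acid start. Censoring needs a caveat, since these patients are selected for low folate.

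The cost is a short amendment and one extra analysis, with no added samples or patients.

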1.1.1 Table of Schedule of Activities

1.1.1 A - PATIENTS WITH NORMAL FOLATE

	SCREENING	CYCLE / /MONTH#1- 3	CYCLE / MONTH #1-3 BIWEEKLY LABS	CYCLE / MONTH #4 +	END OF TREATMENT (1 MONTH POST STUDY TREATMENT
Physical exam	X	X	X	X	X
Medical history	X	X			
Prior treatment	X	X	X		
Prior history of anemia	X	X	X		
Con Meds	X	X	X	X	X
Adverse effects	X	X	X	X	X
CBC w/ diff	X	X	X	X	
CMP	X	X		X	
Pt/PTT/INR*	X ¹				
Urinalysis*	X ¹				
Urine pregnancy test	X ¹	X ¹			
Reticulocyte count	X				
Ferritin	X				
B-12	X				

Clinical Study Protocol - 6
 Olaparib - ESR-18-13807

Folate	X	X	X	X	X
LDH					
Methylmalonic Acid					
Homocysteine					

1. If clinically indicated

1.1.1 B - PATIENTS WHO DEVELOP FOLATE DEFICIENCY

	CYCLE/ MONTH X DAY X + FOLATE DEFICIENCY IDENTIFIED RETURN IN 2 WKS	CYCLE/ MONTH X DAY #1	CYCLE/ MONTH X (IF Hgb less than 10.0 g/dl) weekly	CYCLE/ MONTH X Biweekly labs (IF HGB is above 10.0 g/dl	END OF TREATMENT (1 MONTH POST STUDY TREATMENT)
Physical exam		X			X
Con Meds		X		X	X
Adverse effects		X		X	X
CBC w/Diff	X	X	X	X	
CMP		X			
Folate	X	X	X	X	X
Ferritin	X				
B-12	X				
Reticulocyte Count	X	X	X	X	
LDH	X				
Methylmalonic Acid	X				

Clinical Study Protocol - 6
 Olaparib - ESR-18-13807

Homocysteine	X				
--------------	---	--	--	--	--

1.2 Synopsis

Protocol Title: A study of serum folate levels in patients treated with olaparib

Rationale:

Olaparib as well as other PARP inhibitors are known to cause hematologic toxicity, most commonly, macrocytic anemia regardless of the cancer type treated. The development of anemia may lead to blood transfusions, dose reductions and delay as well as drug discontinuation¹. The cause of anemia is poorly understood. We have observed folate deficiency (<7 ng/mL) in 66% of patients treated with olaparib in a small group of patients with advanced ovarian and metastatic breast cancer occurring within weeks of treatment initiation with olaparib^{2,3}. Folate deficiency is a known cause of macrocytic anemia. However, it has not been previously reported in association with olaparib therapy. In our cohort of patients, folic acid replacement allowed us to avoid or decrease the need for blood transfusions, olaparib dose reduction and discontinuation of therapy.

Statistical methods:

[figure not shown]
A previous study by Rush investigators observed folate deficiency (<7 ng/mL) in 66% of patients treated with olaparib^{2,3}. Under this framework, a sample size of n=60 is calculated using one-sided test to have 80% power in detecting more than half (50%) of the patients having folate deficiency at 0.05 significance level. Allowing for 20% attrition, we propose a sample size of n=75 for this study. The statistical analysis will provide descriptive summaries of the primary endpoint of drug-induced folate deficiency as well the endpoint of response rate and other secondary endpoints. The significance of the observed percentage of folate-deficient cases will be assessed by statistical hypothesis test, as well as by multivariable analysis of the binary endpoint of folate deficiency adjusted by important covariates. The secondary endpoint of response rate to olaparib will be compared between the group who develop cytopenias, folate deficiency, and receive folic acid supplementation and the comparator group by descriptive summaries as well as by statistical hypothesis test. Statistical analysis will be performed in the R Statistical software. No adjustment for multiplicity will be made. Even though the sample size of 75 is optimal to achieve primary and secondary objectives, it would be reasonable to initially accrue 30 patients and re-evaluate the need for continued accrual based on the percentage of patients who develop folate deficiency in this first phase.

[figure not shown]

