1.4 Study rationale

See Section 1.2.

We have observed folate deficiency in 66% of patients of patients with advanced ovarian and metastatic breast cancer occurring within weeks of treatment initiation with olaparib^{2, 3}. While folate deficiency is a known cause of macrocytic anemia, it has not been previously reported in association with olaparib therapy. Since macrocytic anemia is a known complication of olaparib treatment regardless of the cancer type treated, folate deficiency can occur in these patients too.

Clinical Study Protocol - 6
Olaparib - ESR-18-13807

This study is conducted to assess the prevalence and timing of folate deficiency in patients with ovarian, breast, pancreatic, prostate, and other cancers that may benefit from olaparib as determined by their treating physicians based on their tumor sequencing or germline results. .

As folic acid supplementation has not been studied prospectively in this patient population, this study will also evaluate, in a randomized fashion, the impact of folic acid supplementation on anemia and need for transfusion as compared to a placebo group (i.e. no folic acid supplementation while on olaparib).

Background

Olaparib is generally well tolerated. For instance, in the clinical trial of maintenance olaparib monotherapy in patients with platinum-sensitive ovarian cancer who had had 2 or more lines of platinum-based chemotherapy (Study 19), adverse reactions led to olaparib dose interruption, reduction and discontinuation in 35 %, 26 %, and 6 % of patients, respectively¹³. Olaparib is known to cause hematologic toxicity. In the pooled analysis of multiple clinical trials, the following hematologic side effects were observed: anemia in 37% of patients, Macrocytosis (elevated mean corpuscular volume) is reported in up to 89% of patients treated with olaparib¹³. The manufacturer recommends monitoring blood counts at baseline and monthly thereafter, interrupting treatment until any hematologic toxicity has resolved to \leq grade 1, with additional evaluation if blood counts do not recover after 4 weeks of treatment interruption, including bone marrow and cytogenetic analyses^{5, 6}. Little is known about the etiology of olaparib-induced hematologic toxicity.

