8.2 Sample size determination

A previous study by Rush investigators observed folate deficiency (<7 ng/mL) in 66% of patients treated with olaparib. A sample size of $n=60$ is calculated using one-sided test to have 80% power in detecting more than half (50%) of the patients having folate deficiency at 0.05 significance level. Allowing for 20% attrition, we propose a sample size of $n=75$ for this study.

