8.4 Statistical analyses

8.4.1 Efficacy analyses

Patients will be monitored for development of anemia and folate deficiency at scheduled time points throughout the course of the study, as described in Section 1.1. Patients who develop \leq G2 cytopenias and folate deficiency will be randomly assigned in a 1:1 ratio to receive folic acid supplementation 1 mg daily or no supplementation. Patients who develop G3 or higher cytopenias and folate deficiency will be started on folic acid supplementation, thus not included in the randomization. For patients who are randomized, we will assess the impact of folic acid supplementation on anemia, need for transfusion, and dose interruption, dose reduction and drug discontinuation of olaparib as compared to those who did not receive/require folic acid supplementation. Additionally, PFS and RR to olaparib will be compared amongst randomized patients relative to folic acid supplementation.

The statistical analysis will provide descriptive summaries as well as 95% confidence intervals for the primary endpoint of drug-induced folate deficiency in addition to response rate and other secondary endpoints. Kaplan-Meier methodology will be used to estimate the PFS curve and estimate of median PFS and corresponding 95% confidence interval will be provided. The significance of the observed percentage of folate-deficient cases will be assessed by statistical hypothesis test, as well as by multivariable analysis of the binary endpoint of folate deficiency adjusted by important covariates. Covariates will include age, race/ethnic group, previous therapy, Hgb prior to olaparib therapy, genetic testing result (*BRCA* carrier status). RR and PFS will be compared to historical controls as a descriptive comparison. Analyses will be reported on the entire combined cohort of patients with solid tumors and also separately for each cancer type. The statistical analysis of the exploratory endpoint will be specified in the SAP. Statistical analysis will be performed in the R Statistical software. No adjustment for multiplicity will be made.

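### The synopsis calls 75 patients optimal for the primary and secondary objectives, but 75 is derived from the primary test alone and no secondary objective is sized

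*Combined protocol and SAP*

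**What the plan says.** The claim stands in the synopsis (Section 1.2, Statistical methods), in the sentence that introduces the option of accruing 30 patients first: "Even though the sample size of 75 is optimal to achieve primary and secondary objectives".

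The calculation precedes it in the synopsis and is repeated in Section 8.2. The assumed rate comes from earlier experience: "A previous study by Rush investigators observed folate deficiency (<7 ng/mL) in 66% of patients treated with olaparib". From that, "a sample size of n=60 is calculated using one-sided test to have 80% power in detecting more than half (50%) of the patients"; alpha is set at 0.05. Then: "Allowing for 20% attrition, we propose a sample size of n=75 for this study". Section 8.2 adds no other calculation.

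The secondary objectives (Section 2) concern the effect of folic acid on serum folate, haemoglobin, transfusion and olaparib interruption, reduction and discontinuation, and also response rate and progression-free survival (PFS). Section 8.4.1 makes these comparisons among randomised patients, who "will be randomly assigned in a 1:1 ratio to receive folic acid supplementation 1 mg daily or no supplementation". The synopsis plans a hypothesis test for response rate. The second hypothesis in Section 8.1 is that folic acid mitigates haematological toxicity. The third is that it leaves olaparib's antitumour effect unchanged, and no margin is given.

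Not everyone is randomised. Section 1.1 (item 6) requires confirmed folate deficiency with haemoglobin below 12 and above 10 g/dl. Section 3.1 gives folate deficiency with haemoglobin below 12 g/dl. Section 8.4.1 gives folate deficiency with cytopenias of grade 2 or lower.

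**The concern.** The synopsis attributes to the design a property that no calculation in the plan supports. The figure of 75 answers a question about one percentage in the whole cohort. The folic acid question is a two-arm comparison in a subset, with several endpoints and no stated target for any of them.

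What is at stake is how a null result would be read. A reader told that 75 is optimal for the secondary objectives could take a non-significant difference in transfusion or haemoglobin as evidence that folic acid does not help. In the same way, a non-significant difference in response rate or PFS could be taken as support for the third hypothesis. In a comparison this small, neither reading would be safe. The decision after 30 patients rests on the deficiency percentage alone, so nothing later in the plan revisits whether the secondary comparisons are large enough.

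**Working it through.** **1. The plan's own figure.** Inputs from Sections 1.2 and 8.2: null 50%, alternative 66%, one-sided 0.05, 80% power, 20% attrition.

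- Normal approximation: n = [(1.645 × √(0.50 × 0.50) + 0.842 × √(0.66 × 0.34)) / 0.16]² = 58.2, so 59.
- Exact binomial at n = 60: reject at 37 or more; one-sided alpha 0.046, power 0.802.
- Attrition: 60 / 0.80 = 75.

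The stated 60 and 75 reproduce, and the primary test accounts for all of the 75.

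**2. Patients available for the folic acid comparison.** Per arm = N × 0.66 × s / 2, where s is the share of folate-deficient patients who meet the randomisation criterion. The plan gives no value for s.

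| s | N = 75 | N = 60 (after 20% attrition) |
|---|---|---|
| 1.00 (most favourable) | 75 × 0.66 / 2 = 24.8, about 25 | 60 × 0.66 / 2 = 19.8, about 20 |
| 0.37 (illustration only) | 24.75 × 0.37 = 9.2, about 9 | 19.8 × 0.37 = 7.3, about 7 |

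The first row uses only the plan's figures. The second borrows the anaemia rate from the background text in Section 1.4 ("the following hematologic side effects were observed: anemia in 37% of patients") and assumes that it applies to deficient patients independently of deficiency. Neither assumption is in the plan.

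**3. What those numbers can show** (two-sided 0.05). The transfusion rates of 40% and 20% are assumed, because the plan gives none. CI half-width = 1.96 × √[(0.4 × 0.6 + 0.2 × 0.8) / m], with m patients per arm.

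| Per arm (m) | Difference detectable with 80% power, t-test | Fisher power, 40% vs 20% | 95% CI half-width |
|---|---|---|---|
| 25 | 0.81 SD | 23% | 25 points |
| 20 | 0.91 SD | 19% | 28 points |
| 9 (illustration) | 1.41 SD | 7% | 41 points |

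By the normal approximation, 40% vs 20% needs 82 per arm for 80% power. For PFS, an assumed hazard ratio of 0.5 needs 66 events, against at most about 50 randomised patients (75 × 0.66 = 49.5).

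**4. Sensitivity to the 66%.** The primary endpoint counts deficiency within three months, whereas Section 1.1 (item 5) starts the pathway to randomisation at any time point. More than 66% could therefore become deficient in the end. If all 75 became deficient and were randomised, there would be 75 / 2 = 37.5 per arm, still less than half of 82.

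**The case against.** The strongest reply is that the study describes itself as a pilot (Section 3.1), that its secondary objectives are to evaluate and assess, and that Section 8.4.1 already promises descriptive summaries with 95% confidence intervals for response rate and the other secondary endpoints. The disputed sentence appears once, in a clause leading up to the 30-patient look, and Section 8.2 says openly what the number was calculated for. This stands as far as it goes. It lowers the harm, and it means that no new request for confidence intervals is needed. It does not support the word optimal, particularly when the synopsis plans a test of response rate and Section 8.1 lists hypotheses of mitigation and of no antitumour effect.

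The power figures also depend on choices that the plan does not make. For 40% vs 20% at 25 per arm, the normal approximation gives 34% instead of Fisher's 23%. An analysis of the repeated haemoglobin measurements might do better than a single t-test. These are fair qualifications, but 34% is still far below 80%.

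Third, parts of Section 2 allow comparison with patients who neither received nor required folic acid. That group is larger, but it differs in whether deficiency or anaemia developed, so the comparison is confounded. It is not sized either.

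A reader might also infer that the plan itself implies 9 per arm. It does not. The 37% is a pooled rate in all treated patients, and independence sits badly with the plan's premise that folate deficiency contributes to the anaemia. Entry is allowed from 10 g/dl, so some patients may already be below 12. Nor is 9 a floor, since attrition takes it to 7.

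**Conclusion.** The statement is unsupported as written and should be narrowed. The primary sample size is correct, and the documents do not bear out a reading that 60 or 75 is miscalculated. Nor does the plan explicitly claim power for the transfusion or haemoglobin comparison. The fault is one sentence that extends adequacy to objectives for which nothing was calculated.

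The size of the gap rests on the plan's 66%, 1:1 allocation and 20% attrition: about 20 to 25 per arm if every deficient patient is randomised, and fewer otherwise. At that size only differences of about 0.8 to 0.9 SD are detectable with 80% power. The 19% to 23% power and the ±25 to 28 points for transfusion rest further on the assumed 40% and 20%. The figures of 9 and 7 per arm are illustrations.

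Two features could shift the picture. The three descriptions of who is randomised do not agree: Section 1.1 keeps patients below 10 g/dl out of randomisation, while Section 8.4.1 admits cytopenias up to grade 2, which Table 8 defines for anaemia as haemoglobin below 10 and down to 8 g/dl. Section 3.1 also gives folic acid to any randomised patient who falls below 10 g/dl with folate deficiency, whatever the assigned arm, which would tend to dilute the contrast.

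**What to change.** - **Section 1.2:** replace the claim with a statement that 75 is sized for the primary objective only. Say that the secondary randomised comparisons, including the response-rate test and the second and third hypotheses in Section 8.1, are exploratory with no claim of adequate power.
- **Sections 1.1, 3.1 and 8.4.1:** reconcile the randomisation criterion. This must come first, because the expected number randomised depends on it. Which criterion is right is for the investigators.
- **Section 8.2:** then give the expected number randomised, before and after attrition, with each assumption labelled (deficiency rate and share meeting the criterion), and the resulting 95% CI half-width for at least one main secondary endpoint.

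The cost is wording and a short calculation, with no added patients. The drawback is that the stated adequacy of the study becomes less favourable.
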